3.2 Randomization and blinding

As VXA-NVV-105 is a Phase 1b, open-label, boost-optimization study to determine the immunogenicity, safety and tolerability of vaccine VXA-G1.1-NN at dose level 1×10^{10} IU ± 0.5 log with varying boosting schedules, neither randomization nor blinding will be applicable for this study. Both subjects and investigators will be aware of individual treatment assignment.

3.3 Study treatments and assessments

Subject participation will last for about 7 months for Cohort 1 (4-week boost vaccination), 8 and 9 months for Cohorts 2 and 3 respectively (Cohort 2: 8-week boost vaccination; Cohort 3: 12-week boost vaccination). Subjects will be followed for 4 weeks after each dose, and through 6 months following the boosting dose. Following confirmation of eligibility during the screening period, subjects will be enrolled and receive their first

dose of study vaccine on Day 1 and their second dose of study vaccine on Day 29, Day 57 or Day 85 depending on their assigned cohort if deemed eligible after pre-dose safety assessments.

Subjects will record any potential symptoms of reactogenicity daily for 1 week after each dose and return to the site to have safety assessments and samples collected for evaluation of immunogenicity. Subjects deemed ineligible for the second vaccination due to acute illness or new medical condition may be reassessed and have a delayed second vaccination within 1 week of their scheduled vaccination visit if the condition resolves. If a subject remains ineligible after the re-assessment, they will complete an Early Termination (ET) visit and then enter the scheduled follow-up period per cohort assignment as outlined in the schedule of events (SoE). All subjects will enter the follow-up period 4 weeks after their last vaccination and will be monitored for serious adverse events (SAEs), adverse events of special interest (AESIs) and new onset of chronic illness (NOCI) through the End of Study. Subjects will also have samples collected for evaluation of immunogenicity as scheduled in SoE.

A detailed description of procedures and assessments to be conducted during the active period of this study is summarized in the Schedule of Events in Table 2 below, with those during the follow-up period summarized in Table 3.

Table 2 – Schedule of Events (Active Period)

Active Period										
	Screen	Study Period	1 – Cohorts 1	, 2, 3						
				Stud	y Period 2 –	Cohort 1				
						Study Peri	od 2 – Cohor	t 2		
								Study Peri	od 2 – Cohort 3	
Study Day	-45d to -1 d	Day 1 (Wk 0)	Day 8 (Wk 1)	Day 29 (Wk 4)	Day 36 (Wk 5)	Day 57 (Wk 8) /ET ¹	Day 64 (Wk 9)	Day 85 (Wk 12)/ET ²	Day 92 (Wk 13)	Day 113 (Wk16)/ET ³
Visit Window (days)		n/a	0	±2	0	±2	0	±2	0	±2
Informed consent	Х									
Inclusion/Exclusion	Х	Х		Х						
Demographics	Х									
Medical history	Х									
Stool for occult blood	Х									
Blood Sample (HBsAg, HCV, HIV)	Х									
Urine drug screen	Х									
Serum Pregnancy Test ^a	Х	Х		x1		X ²		x ³		
Physical examination	Х	Xb	xb	xb	Xb	xb	Xb	xb	Xb	Xb
Vital Signs	Х	Х	Х	Х	Х	Х	Х	Х	Х	Х
Safety laboratory tests	Х	Xc	Х	Х	Х	Х	Х	Х	Х	Х
Urinalysis	Х	Х	Х	Х	Х	Х	Х	Х	Х	Х
COVID vaccination status	Х									
Vaccination		Х		X ^{1, d,e}		X,2, d,e		x ^{3, d,e}		
Dispense Solicited Symptom Diary		x ^{1,2,3}		x ¹		X ²		x ³		
Review & Collect Solicited Symptom Diary			Х		x1		x ²		X ³	
Review prior & concomitant medication	Х	Х	Х	Х	Х	Х	Х	Х	Х	Х
Query for AEs, SAEs, AESIs andNOCIs		Х	Х	Х	X ^{1,f}	x ^{1,f}	x ^{2,f}	X ^{2,f}	X ^{3,f}	x ^{3,f}
Sample Collection Immunogenicity Assessments	·								-	•
Serum		x ^{1,2,3^g}		x ^{1,2,3}		x ^{1,2}		x ^{2,3}		x ³
Whole blood (Flow-Based)		x ^{1,2,3}	x ^{1,2,3}	x ¹	x ¹	x ²	x ²	x ³	x ³	
Whole blood (PBMC)		x ^{1,2,3}	x ^{1,2,3}	X ¹	X ¹	x ²	x ²	x ³	x ³	
Nasal Swab (Sam Device)		x ^{1,2,3}		x ^{1,2,3}		x ^{1,2}		x ^{2,3}		x ³
Saliva Sample		x ^{1,2,3}		x ^{1,2,3}		x ^{1,2}		x ^{2,3}		x ³

Vaxart Biosciences, Inc.; VXA-NVV-105

Version: Final v2.0, Date: 18-AUG-2021

¹ = Cohort 1; ² = Cohort 2; ³ = Cohort 3.

^a For women of childbearing potential. Test at Day 1 and at second dose (boost). Test at 2nd Study drug administration visit can be serum or urine test.

^b Targeted.

^c If screening lab tests are performed within 2 days prior to dosing, no need to repeat at Day 1.

^d Assess eligibility to receive second dose. Participants with acute illness or new medical condition may be re-assessed, and if the condition resolves, have a delayed 2nd dose within 1 week of scheduled visit.

^e If participants are not eligible to receive their 2nd dose, they immediately enter the follow-up period.

f AEs will only be collected for 4 weeks following each study drug administration.

^g An aliquot of serum collected at baseline will be stored for testing (e.g. Platelet Factor 4 [PF4] antibody ELISA) should an AESI related to blood clots be reported anytime during the study period.

Table 3 – Schedule	of Events	(Follow-up Period)
--------------------	-----------	--------------------

Follow-Up Period						
COHORT 1 COHORT 2 COHORT 3						
Study Day	Months 3, 4, 5, 6	Month 7 (Wk 28)/ EOS	Months 4, 5, 6, 7	Month 8 (Wk 32)/EOS	Months 5, 6, 7, 8	Month 9 (Wk 36)/EOS
Telephone Visit	Х		Х		Х	
Visit Window (days)	±7	±7	±7	±7	±7	±7
Query for SAEs, AESIs and NOCIs	Х	X	Х	Х	Х	Х
Sample Collection Immunogenicity Asses	ssments					
Serum		Х		Х		Х
Whole blood (PBMC) ^a		Х		Х		Х
Nasal Swab (Sam Device)		Х		Х		Х
Saliva		Х		X		Х

AE, adverse event; AESI, Adverse event of special interest; EOS, End of Study; ET, Early Termination; HCV, Hepatitis C Virus; HIV, Human Immunodeficiency Virus; NP,

Nasopharyngeal; NOCI, New Onset of Chronic Illness; PBMC, peripheral blood mononuclear cells; SAE, serious adverse event.

^a Optional.

4.0 Study Endpoints

- 4.1 **Primary endpoints**
 - Number of VP1 specific IgA antibody secreting cells (ASC) by enzyme-linked immunospot (ELISpot) by treatment group and visit
 - Geometric mean titer (GMT) and geometric mean fold rise (GMFR) over the initial GMT of Norovirus G1.1 histo-blood group antigen (HBGA) blocking antibodies (BT50) by treatment group and visit
 - Geometric mean (GM) and GMFR over the initial results of VP1 specific serum IgG by Meso Scale Discovery (MSD) by treatment group and visit

4.2 Secondary endpoints

- Frequencies, durations, and severities of solicited symptoms of reactogenicity (local, systemic) for 1 week following each dose of study drug by treatment group
- Frequencies, durations, and severities of unsolicited AEs, SAEs, AESIs and NOCIs through each active study period (4 weeks post each vaccination) by treatment group
- Number and percentages of subjects with ≥2-, 3-, 4-fold increase over baseline titer of Norovirus G1.1 HBGA BT50 results by treatment group and visit
- Geometric Least Square Mean (LSM) of post-dose Norovirus G1.1 HBGA BT50 titer by treatment group and visit adjusted for baseline titer level
- Least Square Geometric Mean Ratio (LS-GMR) of post-dose titer Norovirus G1.1 HBGA BT50 between treatment groups by visit adjusted for baseline titer level

4.3 Exploratory endpoints

- Frequencies of clinically significant abnormalities in laboratory parameters (chemistry, hematology and urinalysis) at 1 week after each study drug dose and in vital signs immediately following each dose by treatment group
- Frequencies, durations, and severities of all SAEs, AESIs and NOCIs through 6 months after the last vaccination by treatment group
- The following additional immunogenicity parameters will be analyzed by treatment group and visit, and will be reported in the CSR:
 - Number of VP1 specific IgG ASC
 - o GM and GMFR over the initial results of VP1 specific serum IgA

Additional exploratory immunogenicity assays not listed above may also be performed to further evaluate the activity of the VXA-G1.1-NN vaccine candidate. The data from such exploratory assays will be reported outside the scope of this SAP.

5.0 Sample Size and Power

No formal sample size calculation was performed for the study. Thirty subjects in total (10 in each cohort) are planned to be enrolled based on experience of a typical Phase I vaccine study.

6.0 Analysis Populations

6.1 Full Analysis Set (FAS)

The FAS will consist of all subjects who have received at least one dose of vaccine VXA-G1.1-NN. Subjects will be included in the analysis according to the cohort to which they are assigned. Subjects who have been enrolled but never received the study vaccine will be excluded from the analysis.

6.2 Safety population (Safety)

Safety population will consist of all subjects who receive at least one dose of study vaccine and will be analyzed according to the cohort to which they belong according to the actual dosing schedule. Subjects who have been enrolled but never received the study vaccine will be excluded from the analysis.

6.3 Per-Protocol population (PP)

The per-protocol population will consist of all subjects in the FAS who received both vaccine doses and are free from major protocol violations that warrant exclusion. Subjects will be included in the analysis according to the cohort to which they are assigned.

6.4 Protocol deviations/violations and exclusions from analysis sets

All violations and exclusions of subjects from analysis sets will be identified and documented prior to data base lock and final analysis, through clinical review input provided by the sponsor, using the following sources of information:

- Supportive subject listings provided by the ICON GPHS statistician based upon data recorded in the CRF
- Protocol deviation logs provided by the site
- Protocol deviation listings provided by the Sponsor

Deviations from the protocol will be classified as to whether or not they are Major Deviations.

The major protocol deviations to be identified and to be included in the body of the CSR will include the following at a minimum, as well as others classified as key during review of all deviations observed:

- Failure to obtain informed consent
- Incorrect dose of vaccine
- Failure to meet eligibility criteria at baseline

7.0 Statistical Considerations and Analysis

7.1 Derived Variables

The below table provides the list of derived variables for demographic and baseline characteristics, various duration derivations, baseline derivation and other important derivations applicable for this study.

Table 4: Derived Variables

Variables	Formula			
Demographic and Baseline Characteristics				
Age at informed consent (in years)	Integer ((date of informed consent – date of birth + 1) / 365.25)			
Body Mass Index	Weight (kg) / height (m)²			
Derivation of Durations				
Study day at any visit	Date of interest – date of first dose of vaccine. One day is added if the difference is ≥ 0 .			
Duration of any events	End date of event – start date of event + 1			
Baseline Derivations				
Laboratory baseline	The baseline value is defined as the last observation prior to or on the date of the first dose of study drug.			
Change from baseline	Post baseline value – baseline			
Percent change from baseline	[(Post baseline value – baseline) / baseline] * 100			
Change from previous visit	Current value – previous value			
Percent change from previous visit	[(Current value – previous value) / previous value] * 100			
Other Derivations				
Geometric mean/geometric, mean titer/geometric mean concentration	Individual values will be transformed via the natural log, mean values along with 95% CIs will be calculated, which will be transformed back to the original scale via exponentiation.			
Geometric mean fold rise	The mean values and 95% CIs of the log ratio of post dose assay values relative to baseline will be calculated, then transformed back to the original scale via exponentiation.			
Geometric least square mean	Least square means and 95% CIs for each treatment group will be calculated from ANCOVA with immunogenicity assay result on log scale at post dose visit as a dependent variable, treatment group as a factor and baseline immunogenicity assay result on log scale as a covariate, which will be then transformed to the original scale via exponentiation.			
Least square geometric mean ratio	Least square mean differences and 95% CIs among treatment groups will be estimated from the abovementioned ANCOVA model, which will be then transformed to the original scale via exponentiation.			

7.2 Handling of missing data and outliers

The extent and pattern of missing data for primary, secondary, and exploratory endpoints will be summarized by cohort and visit date with frequencies and percentages. No imputations will be conducted for missing data other than dates. No outliers will be eliminated.

7.3 Missing data analysis methods

Imputation rules for missing or partial adverse event start/stop dates

- If the AE start date day is missing (month and year provided) then set the date to the first of the month, unless the month and year are the same as the first dose of study drug. In this case, set the date to the date of first dose.
- If the AE start date month is missing (year is provided) then set the month and day to January 1, unless the year is the same as the year of the first dose. In this case, set the date to the date of first dose.
- If the AE end date day is missing (month and year provided) then set the date to the last day of the month.
- If the AE end date month is missing (year is provided) then set the date to December 31 or current date, whichever is earlier.
- If the year of the AE start date or AE end date are missing, then a query to the site must be made to
 gather additional information. If the end date and start date are both missing, then no imputation will
 be done. If the start date remains missing but the end date is before first dose date, then the AE will
 be considered before treatment and it will not be recorded as an AE in CRF but included as medical
 history. If the end date is after the first dose, then the AE will be considered to have been treatment
 emergent.

Imputation rules for missing or partial medication start/stop dates

Start Date:

- If only day is missing, use the first day of the month.
- If day and month are missing, use the first day of the year.
- If day, month, and year are missing use the first day of the year with the same year as the first dose.

End Date:

- If only day is missing, use the last day of the month.
- If day and month are missing, use the last day of the year.
- If day, month, and year are missing assign 'continuing' status to the stop date.

ICON

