- Unsolicited AEs are any AEs reported spontaneously by the participant, observed by the study personnel during study visits or those identified during review of medical records or source documents. Unsolicited AEs (all AEs not collected in the Solicited Symptom Diary during the first week following each study drug administration) will be monitored and collected from the time of each dose through 4 weeks post each dose.
- Solicited AEs are predefined systemic signs and symptoms of reactogenicity for which the participant is specifically questioned, and which are noted by the participant in their Solicited Symptom Diary, including:
 - fever (any temperature 100°F or higher)
 - headache
 - myalgia (muscle pain)
 - abdominal pain
 - anorexia (defined and not eating)
 - nausea
 - vomiting
 - diarrhea
 - malaise/fatigue

Participants will utilize a Solicited Symptom Diary issued on the day of each study drug administration to record solicited AE daily for the 1 week following each dose.

Table 8Events Meeting Definition of AE

Events Meeting the AE Definition

- Any abnormal laboratory test results (hematology, clinical chemistry, or urinalysis) or other safety assessments (e.g., vital signs measurements) that worsen from baseline and are considered clinically significant in the medical and scientific judgment of the investigator.
- Exacerbation of a chronic or intermittent pre-existing condition including either an increase in frequency and/or intensity of the condition.
- New conditions detected or diagnosed after study drug administration even though it may have been present before the start of the study.
- Signs, symptoms, or the clinical sequelae of a suspected intervention- intervention interaction.
- Signs, symptoms, or the clinical sequelae of a suspected overdose of either study intervention or a concomitant medication. Overdose per se will not be reported as an AE/SAE unless it is an intentional overdose taken with possible suicidal/self-harming intent. Such overdoses should be reported regardless of sequelae.

Events **NOT** Meeting the AE Definition

- Events that occurred from consent to pretreatment
- Medical or surgical procedure (e.g., endoscopy, appendectomy): the condition that leads to the procedure is the AE.
- Situations in which an untoward medical occurrence did not occur (social and/or convenience admission to a hospital).

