8.7.1 Adverse events

All adverse events (AEs) (except for solicited AEs) will be classified by primary SOC and preferred term according to the Medical Dictionary for Regulatory Activities (MedDRA) Version 24.0

AEs will be categorized by solicited AEs, unsolicited AEs (including both AESIs and NOCIs) and SAEs, where the frequencies and durations of each will be summarized by cohort, severity and relatedness to study treatment.

Solicited AEs are predefined systemic signs and symptoms of reactogenicity for which the subjects are specifically questioned; including fever (any temperature 100°F or higher), headache, myalgia (muscle pain), abdominal pain, anorexia (defined as not eating), nausea, vomiting, diarrhea and malaise/fatigue. Frequencies and percentages for each solicited symptom will be calculated. Severities of solicited AEs will be graded according Appendix 1. Definitions of AE, AESI and NOCI are provided in the study protocol (refer to Tables 7 – 11 in the study protocol Section 10.3).

Unsolicited AEs will be summarized by SOC and preferred term for AESIs and NOCIs combined where the events will be sorted by descending overall frequency within each SOC and preferred term according to the total number of events.

Frequencies and percentages of SAEs will be summarized by treatment group, along with specifics including whether the AE is associated with a congenital anomaly or birth defect, whether the AE results in persistent or significant disability or incapacity, initial or prolonged hospitalization, and death, whether the AE is life-threatening, or medically important but not covered by other serious criteria.

The severity of AEs will be assessed by the clinician using a protocol-defined grading system. For events that are not listed in the protocol-defined grading system, refer to Table 12 in the study protocol Section 10.3 for classifying severity.

Relationships of AEs to study vaccine are categorized as not related, possibly related, probably related, and definitely related (refer to Table 17 in the study protocol Section 10.3.1 for details).

Details for imputing missing or partial start dates of adverse events are described in Section 7.2 of this SAP.

ICON

Where a subject has the same adverse event, based on preferred terminology, reported multiple times in the treatment period, the subject will only be counted once at the preferred terminology level in adverse event frequency tables.

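### SAP 7.3 imputes partial AE start dates with reference to Dose 1 only, so day-missing AEs that begin after Dose 2 in the Dose 2 calendar month are dated before Dose 2

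*SAP*

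**What the plan says.** SAP 7.3 gives two rules for an incomplete AE start date. With the day missing, "set the date to the first of the month, unless the month and year are the same as the first dose of study drug"; in the excepted case the Dose 1 date is used. With the month missing, the start becomes 1 January "unless the year is the same as the year of the first dose", and again the Dose 1 date is the fallback. For stop dates: "If the AE end date day is missing (month and year provided) then set the date to the last day of the month". Protocol 9.2.1 leaves missing AE dates to the SAP, so no other rule applies.

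Three places use the result:

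- SAP 4.2 makes unsolicited AEs, SAEs, AESIs and NOCIs a secondary endpoint "through each active study period (4 weeks post each vaccination) by treatment group".
- SAP 7.1 derives duration as "End date of event – start date of event + 1".
- SAP 8.7.1 sorts AEs into solicited, unsolicited and serious, "where the frequencies and durations of each will be summarized by cohort, severity and relatedness to study treatment".

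SAP 8.7.1 also says: "Details for imputing missing or partial start dates of adverse events are described in Section 7.2 of this SAP". The rules are in 7.3. Solicited symptoms are outside the problem, because Protocol Appendix 3 (Table 7) has participants "record solicited AE daily for the 1 week following each dose".

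**The concern.** A rule anchored to the first dose suits a single-dose study. Here each participant has two at-risk periods, and a start date known only to the month can lie on either side of the second dose. The SAP resolves that ambiguity the same way every time, towards the date before Dose 2.

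Two outputs could be affected. The first is duration, which uses the imputed start directly. The second is the dose period to which an event belongs. Safety by boost schedule is the secondary objective, and the interval between doses differs by cohort, so a backdated event lands in a different place in each cohort. With 10 participants per cohort, one misplaced participant moves a by-dose incidence by 1/10 = 10 percentage points.

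**Working it through.** The documents give no figure for misdated AEs, so there is none to reproduce. The check applies the SAP 7.3 rule by calendar date.

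**Inputs from the documents.** Dose 2 is 28, 56 or 84 days after Dose 1 for Cohorts 1, 2 and 3 (SAP 8.5). Each period is 4 weeks after a dose (SAP 4.2).

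**Assumptions.** Onset is uniform over days 0 to 27 after Dose 2. First doses are spread evenly over 1 April to 25 August 2021 (147 days), between the original protocol date and the amendment that reports enrolment complete. This gives 147 × 28 = 4116 combinations per cohort.

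**Illustration (invented dates).**

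- Cohort 2: Dose 1 on 10 May, Dose 2 on 5 July, AE begins 20 July but is recorded as July. The imputed start is 1 July, 4 days before Dose 2 and after the Dose 1 period ended on 6 June. The start is 19 days too early.
- Cohort 1: Dose 1 on 10 May, Dose 2 on 7 June, AE begins 20 June. The imputed start is 1 June, inside the Dose 1 period and again 19 days too early.

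**Share dated before Dose 2.** In a simple 30-day month, 434/840 = 51.7%. On the 2021 calendar:

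| Cohort | Before Dose 2 | In Dose 1 period | Outside both periods |
|---|---|---|---|
| 1 | 2221/4116 = 54.0% | 2221 | 0 |
| 2 | 2203/4116 = 53.5% | 11 | 2192 (53.3%) |
| 3 | 2191/4116 = 53.2% | 0 | 2191 (53.2%) |

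The last two columns assume assignment by imputed start date and on-time dosing. With Dose 2 given 7 days late, 809/4116 = 19.7% of the Cohort 1 events also fall outside both periods.

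**Sensitivity to onset.** For onset in days 8 to 27 or 8 to 28 the share is 38% to 41%, depending on the calendar used. For onset in days 0 to 6 it is 86% to 87%.

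**Sensitivity to accrual.** Suppose first doses stop early enough for every subject to have entered the follow-up period by 25 August (30 June, 2 June and 5 May for Cohorts 1, 2 and 3). The shares become 53.2%, 51.3% and 49.4%. If a cohort's first doses all fall within two weeks, the share ranges from 23% to 83% with the dates.

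**Duration.** Excess = true onset minus imputed start. The mean over moved events is 19.9 days in each cohort (median 21). Setting the start to the Dose 2 date instead leaves a mean excess of 9.6 days (median 8).

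**Month missing.** For first doses in this 2021 range every such AE goes to the Dose 1 date, so all are dated before Dose 2. Such dates should be rare.

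**Why a Dose 2 clause needs a guard.** In Cohort 1, 2107/4116 = 51% of day-missing AEs that truly belong to the Dose 1 period also lie in the Dose 2 month; in Cohorts 2 and 3 the counts are 11 (0.3%) and 0. An imputed end date cannot separate them, because the month end never precedes a Dose 2 in that month.

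**The case against.** The strongest reply is that no stated analysis is shown to break. SAP 8.7 summarises safety data by cohort and study visit, and the table templates are in a separate document. If AEs are placed by reporting visit, the imputed day does not affect placement. A reader might infer that post-boost AEs in Cohorts 2 and 3 drop out of the secondary endpoint and that the rule creates a safety difference between schedules. The documents do not support that as a certainty: no passage says that periods are assigned by imputed start date. Moreover, footnote f to the schedule, Protocol 8.2 and Table 7 limit unsolicited AE collection to 4 weeks after each dose. An imputed date between the periods would then look plainly wrong and could be caught.

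The second reply is that partial dates may be very few, or none, in a single-centre study of 30 with on-site visits, source verification and data cleaning. That is fair.

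The third is that percentages to one decimal place rest on assumed onset and accrual; SAP 3.1 in fact has Cohorts 3 and 2 enrolled before Cohort 1. That also stands, and only the rough share should be relied on.

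A reader might also take the blank AE query cells at the Dose 2 visit for Cohort 2 (Day 57) and Cohort 3 (Day 85) to mean lost events. They do not show that. Examination, vital signs, laboratory tests and medication review are marked at those visits, pre-dose safety assessments are required, and Table 5 makes SAE, AESI and NOCI reporting continuous.

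What survives is that the stated rule gives a wrong start date for a definable class of events, and that duration carries the error wherever the event is tabulated.

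**Conclusion.** The gap is real and minor. Roughly half of day-missing AEs beginning in the 4 weeks after Dose 2 would be dated before Dose 2 if onset is uniform; about 40% if onset falls after the first week, and about 87% if within it. Their durations, summarised by cohort, are overstated by about 20 days on average under the uniform assumptions.

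The effect on dose periods is conditional. If imputed start dates decide the period, the events fall in the Dose 1 period for Cohort 1 with on-time dosing, and almost always outside both periods for Cohorts 2 and 3.

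Fully dated AEs, diary symptoms and by-cohort counts not cut to the 4-week windows are unaffected. If no start date is partial, nothing changes. Confidence is moderate, because the number of partial dates and the assignment rule are both unknown.

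**What to change.** Before database lock:

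1. In SAP 7.3, where the known part of a start date fits Dose 2 as well as an earlier period, impute the Dose 2 date. Keep the existing rule if a complete, non-imputed end date precedes Dose 2, or if the record shows that the event was reported before Dose 2.
2. Where the record does not settle it, including where both doses fall in one month, flag the event and show it under both assignments.
3. In SAP 8.7.1, state that unsolicited AEs are assigned to a dose period by start date, report the number of imputed start dates by cohort, and correct the cross-reference from 7.2 to 7.3.

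The cost is a few sentences of SAP text and no new visits or data. The downside is that some pre-Dose-2 events without a complete end date could be moved to Dose 2, mainly in Cohort 1. If a share L of that cohort's day-missing Dose 1-period AEs has neither a complete end date nor a record of earlier reporting, about L × 0.51 is exposed: 2.6%, 5.1% or 10.2% for L = 5%, 10% or 20% (assumed). The flag in item 2 makes these visible. Durations of moved events would still be overstated, by about 10 days instead of 20.

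Two wording conflicts should be reconciled separately:

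- the AE query row, blank at Day 57 for Cohort 2 and Day 85 for Cohort 3 in both schedules;
- Table 5's single continuous window for unsolicited AEs, against the 4 weeks after each dose in footnote f, Protocol 8.2 and Table 7. If Table 5 prevails, events between doses in Cohorts 2 and 3 would also need the flag.

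### Partial adverse-event end dates are imputed late and not excluded from duration, so a short event with a partial end date can be reported as lasting weeks or months

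*SAP*

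**What the plan says.** SAP 7.3 gives two rules for partial end dates of adverse events.

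- Day missing: "If the AE end date day is missing (month and year provided) then set the date to the last day of the month".
- Month missing: "set the date to December 31 or current date, whichever is earlier".

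Partial start dates move the other way, to the first of the month or 1 January. If that month or year is also that of the first dose, the rule is "In this case, set the date to the date of first dose". A missing year goes to a site query, and nothing is imputed when start and end are both missing.

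Table 4 in SAP 7.1 defines the variable "Duration of any events" as "End date of event – start date of event + 1", with no exception for imputed dates. SAP 7.2 adds "No imputations will be conducted for missing data other than dates" and "No outliers will be eliminated".

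Duration is an endpoint component: SAP 4.2 lists "Frequencies, durations, and severities of unsolicited AEs, SAEs, AESIs and NOCIs through each active study period" among the secondary endpoints. SAP 8.7.1 summarises durations by cohort, severity and relatedness. The statistical section of the protocol (9.2.1) leaves the handling of missing AE dates to the SAP, so no other text overrides these rules.

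**The concern.** The latest possible end date is a cautious choice when the question is whether an event overlaps treatment. It is a poor choice for measuring how long the event lasted, because the error always lengthens the duration. The plan does not separate the two uses.

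The month-missing rule also depends on a date that the SAP does not tie to data cut, database lock, last contact or End of Study. If it is read as the day the program runs, a table produced before 31 December of the year in question may not be reproducible later.

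At stake is the descriptive duration summary for unsolicited AEs, SAEs, AESIs and NOCIs. Each cohort has 10 participants, so a single long value can carry the mean and the maximum.

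**Working it through.** The plan states no figure on this point, so there is none to reproduce. The check applies the SAP 7.3 rules and the Table 4 formula to short events.

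**Inputs.** Rules and formula are from SAP 7.3 and 7.1. The calendar is 2021: the original protocol is dated 31 March 2021, and the amendment of 25 August 2021 says enrolment was complete. The exact dates below, and their even spread over April to December (four months of 30 days, five of 31, 275 days in all), are assumptions.

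**End day missing, event within one month.** Reported duration = D − s + 1, with D the days in the month and s the start day. For a true length L, s runs from 1 to D − L + 1, so the monthly mean is (D + L)/2 over D − L + 1 start days.

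- L = 1: (4 × 30 × 15.5 + 5 × 31 × 16) / 275 = 4340/275 = 15.8 days.
- L = 3: (4 × 28 × 16.5 + 5 × 29 × 17) / 257 = 4313/257 = 16.8 days.
- L = 7: (4 × 24 × 18.5 + 5 × 25 × 19) / 221 = 4151/221 = 18.8 days.

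**End day missing, event may cross a month end.** For a true 3-day event, reported duration = 2 + (D − e + 1), with e the end day. The mean is 2 + 15.8 = 17.8 days and the range is 3 to 33. The value is 14 days or more for (4 × 19 + 5 × 20)/275 = 176/275 = 64% of end days. An event ending on the last day of a month gains nothing.

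**Start and end day both missing, same month, not the first-dose month.** The whole month is reported: 30 days for June, 31 for July.

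**End month missing.** Reported duration = min(31 December, current date) − start + 1.

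- Start 10 June 2021, end set to 31 December: 21 + 31 + 31 + 30 + 31 + 30 + 31 = 205 days. This needs a current date on or after 31 December 2021; an earlier one gives fewer days.
- True event 3 to 5 June 2021: 77 days if the current date is 18 August 2021, 121 days if 1 October 2021, and 212 days from 31 December 2021 on. With only the end day missing, it is 28 days.

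**No cap.** If a Cohort 1 participant was first dosed on 1 June 2021 (assumed), the Week 28 End of Study visit falls 196 days later, on 14 December 2021 (±7 days). An imputed end of 31 December lies beyond that visit.

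**Effect on a cohort summary.** Take ten events, nine of 3 days with complete dates and one 3-day event imputed as above.

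| Imputed value | Mean (true mean 3.0) | Median | Maximum |
|---|---|---|---|
| 28 days | (27 + 28)/10 = 5.5 | 3 | 28 |
| 121 days | (27 + 121)/10 = 14.8 | 3 | 121 |
| 212 days | (27 + 212)/10 = 23.9 | 3 | 212 |

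**The case against.** The case for leaving the rule alone has real substance.

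- Only partial end dates are affected, and the documents do not say how many to expect. A missing year is queried. With daily diaries, site visits and SAE reporting within 24 hours, a missing month should be rare.
- SAP 8.1 asks for median and IQR as well as mean and maximum, and the median is robust as long as most of the events summarised carry complete dates. Listings show individual durations, so an extreme value can be traced. SAP 7.2 already summarises the extent of missing data.
- No test or decision rule uses duration. AE counts and severity grades do not depend on the end date.

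All of this stands and limits the weight of the point. It does not remove it, because the text as written still gives the inflated value.

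Three stronger readings are tempting, and the documents do not support them.

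- A reader might infer that every affected AE would show one duration in the CSR and another in the addendum. SAP 8.8 limits the follow-up update to SAE and immunogenicity outputs, so between those two reports only SAE tables could change. Once the current date has passed 31 December of the recorded year, the imputed value is fixed.
- A reader might take the current date to be the program's run date. That is the plain reading, but the SAP does not define the term; the supportable criticism is that it is undefined.
- A reader might extend the point to intermittent diary symptoms, on the ground that end minus start counts symptom-free days. That does not concern imputed dates. Protocol Section 9.2.1 says missing diary data are not imputed, and the protocol's severity table (Table 12) calls for onset and duration of each episode of an intermittent event.

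**Conclusion.** The point holds as a minor one. For an unsolicited AE, SAE, AESI or NOCI with a partial end date, the stated rules can turn a few days into weeks (day missing: about 17 to 18 days on average for a true 3-day event) or months (month missing: up to 205 days for a 10 June 2021 start). One month-missing record can dominate a cohort's mean and maximum; a day-missing record does much less.

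The sizes rest on the assumed 2021 dates, an even spread of events over the calendar, and an illustrative ten events per cohort. That imputed dates enter duration follows from the absence of any exclusion in Table 4; the SAP does not say so outright. The documents do not show that many records would be affected, so the effect on the actual tables is unknown and may be small.

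**What to change.** Change the SAP wording in three places.

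1. In 7.3, state that imputed AE dates serve only to classify events as treatment-emergent.
2. In Table 4, state that duration is missing when the start or end date was imputed, and report the number of such events per cohort beside the duration summary.
3. In 7.3, replace the current date with the participant's last contact or End of Study date, so that the month-missing rule takes the earlier of that date and 31 December. Apply the same cap to the day-missing rule. Once item 2 is in place the cap no longer affects duration; it keeps listings and classification within the observed period and makes them reproducible.

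While editing, correct the cross-reference in 8.7.1, which sends the reader to 7.2 for AE date imputation although the rules are in 7.3.

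No new data are needed. The cost is that a few durations become missing, and the count in item 2 shows how many.
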